7.2.2. Clinical Laboratory Evaluations

Clinical laboratory evaluations (clinical chemistry panel [fasted at least 8 hours], coagulation parameters, CK, CBC, TSH, HbA1c [Screening only], and UA) will be collected at the timepoints specified in Appendix 4.

Screens for HCV antibody, HBsAg, and HIV antibody will be performed at Screening. A urine drug screen for selected drugs of abuse (including cotinine) and an alcohol breath test will be performed at Screening and repeated at Check-in (Day -1) for all subjects. A serum qualitative pregnancy test (female subjects only [serum quantitative may be used for confirmation if needed]) and an FSH test (post-menopausal female subjects only) will be performed at the timepoints specified in Appendix 4.

The number of blood samples and total blood volume required for clinical laboratory evaluations is presented in Appendix 3. A list of the specific evaluations is in Appendix 2.

7.2.3. Vital Signs

Vital signs (including oral temperature, respiratory rate, and supine BP, and pulse rate) will be obtained at the timepoints specified in Appendix 4.

Blood pressure and pulse rate measurements should be performed using the same arm for each reading and measurements should be taken after the subject has been resting in the supine position for at least 5 minutes.

When vital signs assessments are scheduled at the same time as blood draws, the blood draws will be obtained at the scheduled timepoint, and the vital signs will be obtained prior to and as close as possible to the scheduled blood draw.

7.2.4. 12-lead Electrocardiogram

A 12-lead ECG (including PR, RR, QRS, and QT interval parameters) will be obtained after the subject has been resting for at least 10 minutes in the supine position at the timepoints specified in Appendix 4. The QT interval will be corrected for heart rate by Fridericia's $(QTcF = QT/[RR]^{1/3})$ formula.

When 12-lead ECGs are scheduled at the same time as blood draws, the blood draws will be obtained at the scheduled timepoint, and the 12-lead ECGs will be obtained prior to and as close as possible to the scheduled blood draw.

7.2.5. Physical Examination

A complete or abbreviated physical examination will be performed at the timepoints specified in Appendix 4. Complete physical examinations will evaluate general appearance and the following body systems/organs: dermatological; head and eyes; ears, nose, mouth, and throat; pulmonary; cardiovascular; abdominal; lymphatic; musculoskeletal/extremities; and neurological. Weight and height will be reported (height only reported during Screening).

Abbreviated physical examinations will evaluate general appearance and the following body systems/organs: dermatological; pulmonary; cardiovascular; abdominal; and neurological.

8. SAMPLE SIZE AND DATA ANALYSIS

8.1. Determination of Sample Size

Twenty-four healthy adult male and female subjects (women of non-childbearing potential only); 12 subjects in Part 1 and 12 subjects in Part 2 to ensure that 20 subjects complete the study. This is a phase 1 study and the sample size is not based upon any formal power calculations but is consistent with previous studies of a similar design.

Each subject will participate in either Part 1 or Part 2, but not both.

Every attempt will be made to enroll at least 3 subjects of each sex in the study.

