To assess their eligibility to enter the study, potential subjects will be screened within 28 days (Days -29 to -2) and be admitted to the Clinical Research Unit (CRU) on Day -1 (Check-in).

Subjects will be confined at the CRU from the time of Check-in (Day -1) until End of Treatment (EOT) on Day 19 upon completion of all PK and safety assessments or Early Termination (ET) if the subject discontinues. A follow-up phone call will occur for all

subjects who received at least 1 dose of study drug (including subjects who are terminated early) 7 days (\pm 2 days) after EOT or ET.

Replacement subjects may be enrolled only if deemed necessary by the Sponsor.

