4. STUDY DESIGN

This is a Phase 1, 2-part study. Each part will be conducted as an open-label, 2-period, fixed-sequence study. Following completion of the sentinel subjects in Part 1, the study parts may be conducted concurrently. Each subject will participate in either Part 1 or Part 2, but not both.

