8.5.3.1. Statistical Analyses

A statistical analysis will be conducted to investigate the drug-drug interaction on the PK of LOXO-305 for AUC₀₋₂₄, AUC_{0-t}, AUC_{0-inf}, and C_{max} . The comparisons of interest are:

Study Part 1:

To access the impact of multiple oral doses of itraconazole on the single oral dose PK of LOXO-305 (AUC_{0-t}, AUC_{0-inf}, and C_{max})

• 200 mg itraconazole co-administered with 200 mg LOXO-305 (test treatment) vs 200 mg LOXO-305 alone (reference treatment).

Study Part 2:

To assess the effect of multiple oral doses of rifampin (strong CYP3A4 inducer) on the single oral dose PK of LOXO-305 (AUC_{0-t}, AUC_{0-inf}, and C_{max}) in healthy adult subjects

• 600 mg rifampin QD co-administered with 200 mg LOXO-305 (test treatment, Day 17) vs 200 mg LOXO-305 alone (reference treatment)

To assess the effect of a single oral dose of rifampin on the single oral dose PK of LOXO-305 (AUC₀₋₂₄, and C_{max})

• 600 mg rifampin once co-administered with 200 mg LOXO-305 (test treatment, Day 8) vs 200 mg LOXO-305 alone (reference treatment)

The ln-transformed³ PK parameters (AUC₀₋₂₄, AUC_{0-t}, AUC_{0-inf}, and C_{max}) will be analyzed using a mixed model.⁴ The model will include actual treatment as fixed effect, and subject as a random effect.

For each PK parameter separately, the least squares mean (LSM) for each treatment, difference in LSMs between the test and reference treatments, and corresponding 90% confidence interval (CI) will be calculated; these values will then be exponentiated to give the geometric least squares mean (GLSM), geometric mean ratios (GMR), and corresponding 90% CI.

Additionally, the pooled estimate (across all treatments) of the within-subject CV will be calculated, and residual plots will be produced to assess the adequacy of the model(s) fitted.

Examples of the SAS code that will be used are as follows:

Mixed Model Analysis

```
proc mixed data = <data in>;
by parcatln parcatl paramn param;
class trtan usubjid;
model lpk = trtan / cl residual ddfm = kr;
lsmeans trtan / cl pdiff = control('1') alpha = 0.1;
random intercept / subject = usubjid;
```

```
ods output lsmeans = <data out>;
  ods output diffs = <data out>;
  ods output covparms = <data out>;
run;
```

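### Is a target of 20 completers over both parts a defect when each part is analysed on its own?

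*Protocol*

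**What the plan says.** Protocol 8.1, repeated in the synopsis and in SAP 5, sets enrolment and a completer target in one sentence: "12 subjects in Part 1 and 12 subjects in Part 2 to ensure that 20 subjects complete the study". It adds that "the sample size is not based upon any formal power calculations but is consistent with previous studies of a similar design". No dropout rate, power, variance or minimum number per comparison is given.

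The parts are separate: "Each subject will participate in either Part 1 or Part 2, but not both" (SAP 4). SAP 8.5.3.1 lists one comparison for Part 1 (itraconazole with LOXO-305 against LOXO-305 alone) and two for Part 2 (rifampin on Day 17 and on Day 8, each against LOXO-305 alone). For each PK parameter, the "difference in LSMs between the test and reference treatments, and corresponding 90% confidence interval (CI) will be calculated". There is no acceptance margin.

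On losses, Protocol 3.1.1 says "Replacement subjects may be enrolled only if deemed necessary by the Sponsor". Protocol 4.5 extends this to subjects with insufficient PK data and gives a numbering rule for replacements. Under Protocol 8.2.1 and SAP 7.3, the PK population needs a LOXO-305 dose, a quantifiable concentration and at least one computable parameter. It does not require completion.

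**The concern.** A completer target should refer to the group that an analysis uses. Here no analysis uses 20 subjects. The total is met by 10 and 10, by 11 and 9, or by 12 and 8, so it protects only 8 completers in the smaller part. Nor can enrolling 12 and 12 ensure 20 completers, because replacement is discretionary and tied to no count.

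The stake is precision in one part. The geometric mean ratio and its 90% confidence interval are the main result for each interaction. If one part ran short while the study total looked satisfactory, that part's interval would be wider and the stated target would give no warning.

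**Working it through.** **Inputs.** From the documents: 12 enrolled per part, 24 in all, 20 completers in all, 90% intervals. Assumed, because the documents give no value: dropout of 5%, 10% or 15%, independent between subjects, with no replacement; within-subject CV of 25% or 40%.

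**The plan's own figures.** 12 + 12 = 24, and 24 − 20 = 4 allowed losses, or 4/24 = 16.7%. The figures agree with each other. No sample size can be re-derived, because none was calculated.

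**Splits of exactly 20 completers.** If 4 of the 24 are lost at random, there are C(24,4) = 10,626 equally likely sets.

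- 10 and 10: C(12,2)² = 4,356, or 41.0%
- 9 and 11: 2 × 12 × C(12,3) = 5,280, or 49.7%
- 8 and 12: 2 × C(12,4) = 990, or 9.3%

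So a study that just reaches 20 has a part below 10 more often than not, but that part is usually at nine.

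**All outcomes that meet the target.** Let X be binomial with 24 trials and Y binomial with 12 trials, each with success probability 1 − dropout. Let A = P(X ≥ 20) and B = P(Y ≥ 10)². Two parts with at least 10 each always total at least 20, so P(a part below 10, given at least 20 in all) = (A − B)/A. A part of exactly eight needs the other to be complete, so P(12 and 8, given at least 20) = 2 × P(Y = 12) × P(Y = 8)/A.

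| Assumed dropout | A | B | Part below 10, given target met | 12 and 8, given target met |
|---|---|---|---|---|
| 5% | 0.994 | 0.961 | 0.033 | 0.002 |
| 10% | 0.915 | 0.791 | 0.136 | 0.013 |
| 15% | 0.713 | 0.541 | 0.241 | 0.027 |

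At 10%, for example, (0.9149 − 0.7906)/0.9149 = 0.136, and 2 × 0.2824 × 0.0213/0.9149 = 0.013. The share of short parts that have nine rather than eight completers is 1 − 0.013/0.136 = 0.90 at 10% dropout and 1 − 0.027/0.241 = 0.89 at 15%.

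**Precision.** For a paired two-treatment comparison, the log-scale half-width is t(0.95, n−1) × s × √(2/n), with s² = ln(1 + CV²). The ratio between two values of n depends only on t/√n.

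- n = 10: 1.833/√10 = 0.580
- n = 9: 1.860/√9 = 0.620, ratio 0.620/0.580 = 1.07
- n = 8: 1.895/√8 = 0.670, ratio 0.670/0.580 = 1.16

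The interval limits, as multiples of the estimated ratio, are:

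| Completers | CV 25% | CV 40% |
|---|---|---|
| 8 | 0.79 to 1.26 | 0.69 to 1.44 |
| 9 | 0.81 to 1.24 | 0.71 to 1.40 |
| 10 | 0.82 to 1.22 | 0.73 to 1.37 |
| 12 | 0.84 to 1.20 | 0.75 to 1.33 |

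**The case for a change.** The strongest case for a change is that the total is the only completer target in the documents, so it is the natural guide when the sponsor decides on replacement, and it can be satisfied while one part is short. Evaluable numbers can also fall below completers: SAP 7.3 allows exclusion for early vomiting, SAP 8.5.1.3 drops AUC extrapolated to infinity when extrapolation exceeds 30%, and SAP 8.5.1.4 allows exclusion for predose values above 5% of Cmax. A subject with Day 1 data only stays in the PK population but adds little to a within-subject ratio. Restating the target per part would cost one sentence.

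What stands is that the target sits at a level no analysis uses and that its verb is too strong. The rest does not carry a change.

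- Ten per part is an inference from an even split. It is stated nowhere, so it cannot be used to show that the stated size is missed. The sentence does give a per-part figure, 12, and Protocol 3.1.1 repeats it for Part 1 as 3 + 9.
- The probabilities above assume no replacement. Protocol 4.5 allows it for both non-completers and subjects with insufficient PK data, and the sponsor will see the count in each part.
- Completion is not what every comparison needs. The Day 8 comparison in Part 2 uses data to 24 hours after dosing, so a subject who leaves before Day 17 still contributes to it. The mixed model keeps partial data.
- The example code in SAP 8.5.3.1 ("by parcatln parcatl paramn param") shows no obvious variable for study part, but the comparisons are listed part by part, so the code gives no reason to think that the parts would be pooled.
- A replacement trigger set at 10 would either repeat what the sponsor may already do or enrol more subjects to meet a number that the plan does not rest on.

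**Conclusion.** This is loose wording, not a failure of the design. The completer target guarantees only 8 in the smaller part, and 12 + 12 with discretionary replacement cannot ensure 20. But no stated per-part completer number, power or precision is missed, and the plan's figures agree with each other.

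Under assumed dropout of 10% to 15% without replacement, the likely shortfall is one subject below ten in one part, with an interval about 7% wider on the log scale. The 16% widening belongs to a split with probability 0.013 to 0.027 among studies that meet the target. At 5% dropout even a part of nine is uncommon (0.033 for any part below 10). These figures rest on assumed dropout rates, independent losses and the paired two-treatment case.

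Whatever the split, each part still yields a valid estimate and 90% interval whose width shows the number actually available, and SAP 8.1 already asks for caution because the size is unpowered. Rewording the target would alter no analysis and no result. If the documents are revised for another reason, an expected number of completers per part would read more clearly; nothing in the plan depends on it.

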8.2. Analysis Populations

8.2.1. Study Populations

The **PK Population** will consist of all subjects who have received a dose of LOXO-305, have at least 1 quantifiable plasma concentration, and for whom at least 1 PK parameter can be computed. A subject may be excluded from the PK summary statistics and statistical analysis if the subject has an AE of vomiting that occurs at or before 2 times median time to maximum concentration.

The **Safety Population** will consist of all subjects who have received at least 1 dose of study drug. Subjects will be classified into groups based on actual treatment received.

8.3. Pharmacokinetic Analysis

In Part 1, serial PK blood samples for the analysis of plasma concentrations of LOXO-305 will be collected from predose through 168 hours postdose following administration of LOXO-305 alone on Day 1 (Period 1) and with itraconazole on Day 12 (Period 2). In Part 2, serial PK blood samples for the analysis of plasma concentrations of LOXO-305 will be collected from predose through 24 hours postdose following administration of LOXO-305 and rifampin on Day 8 (Period 2) and from predose through 168 hours postdose following administration of LOXO-305 alone on Day 1 (Period 1) and with rifampin on Day 17 (Period 2).

Whenever possible, the following PK parameters will be calculated for each subject, based on the plasma concentrations of LOXO-305 (as appropriate):

AUC ₀₋₂₄	area under the concentration-time curve from Hour 0 to 24 hours postdose, as calculated by the linear trapezoidal method (for Day 1 and Day 8 of Part 2 PK only)	
AUC _{0-t}	area under the concentration-time curve (AUC) from Hour 0 to the last measurable concentration, calculated using the linear trapezoidal rule for increasing and decreasing concentrations	
AUC _{0-inf}	AUC extrapolated to infinity, calculated using the formula:	
	$AUC_{0-inf} = AUC_{0-t} + \frac{C_t}{\lambda_z}$	
	where C_t is the last measurable concentration and λ_Z is the apparent terminal elimination rate constant	
%AUC _{extrap}	percentage extrapolation for AUC	
C _{max}	maximum observed plasma concentration	
t _{max}	time to maximum observed concentration	
λz	apparent terminal elimination rate constant, where λ_Z is the magnitude of the slope of the linear regression of the log concentration versus time profile during the terminal phase	
CL/F	apparent systemic clearance	
t1/2	apparent terminal elimination half-life (whenever possible), where $t_{1/2} = ln(2)/\lambda_Z$	
Kel	apparent first-order terminal elimination rate constant Additionally, the number of points used to estimate λ_z will be presented in a listing.	

Pharmacokinetic calculations will be performed using commercial software such as Phoenix[™] WinNonlin[®] Version 8.1 or higher (Certara USA Inc.).

Other parameters may be added as appropriate. Final PK parameters reported will be detailed in the Statistical Analysis Plan (SAP).

Pharmacokinetic analysis will use actual times as recorded on the eCRF. All statistical analysis will be performed using SAS[®] Version 9.3 or greater. More details on the analyses will be included in the SAP.

8.3.1. Descriptive Analysis

Plasma concentrations and PK parameters will be summarized with descriptive statistics (number, arithmetic mean, standard deviation, coefficient of variation [CV%], geometric mean, geometric CV%, median, minimum, and maximum).

8.3.2. Statistical Methodology

The primary analysis planned for this study is a mixed effect model that includes treatment as a fixed effect and subject as a random effect. The analysis will be performed on the ln-transformed PK parameters (AUC_{0-t}, AUC_{0-inf}, and C_{max}) and include calculation of least squared (LS) means and the difference between treatment LS means, as well as their corresponding 90% confidence intervals (CIs). The ratios and their 90% CIs of the PK parameter for each treatment comparison will be constructed using the exponentiation of the difference and the CIs from the mixed effect model.

8.4. Safety Analysis

All safety assessments, including AEs and SAEs, vital signs measurements, clinical laboratory results, physical examination results, concomitant medications, and 12-lead ECGs, will be tabulated and summarized where possible, using descriptive methodology, as needed, by timepoint. Unless otherwise specified, baseline value is defined as the last non-missing measurement before administration of LOXO-305 in each period. No formal statistical analyses are planned for the safety data. All safety data will be listed by subject.

Concomitant medications will be coded using the World Health Organization (WHO) Drug Dictionary (WHO Drug Global B3, 01 March 2019). The incidence of AEs will be presented by severity and by relationship to study drug as determined by the Investigator (Appendix 1 for AE reporting). All TEAEs will be summarized by SOC and PT, using MedDRA Version 22.0.

8.5. Data Handling and Record Keeping

Any changes to information in the trial progress notes and other source documents will be initialed and dated on the day the change is made by a CRU staff member authorized to make the change. Changes will be made by striking a single line through erroneous data and clearly entering the correct data (eg, wrong data right data). If the reason for the change is not apparent, a brief explanation for the change will be written adjacent to the change by the clinician.

The Data Management Plan will be approved by the Sponsor.

Data will be validated during data entry by the CRU and verified by the Study Monitor. Data will then be reviewed by the data management group to resolve any outstanding issues. Listings will be generated after the database is cleaned by data management and will be reviewed by the Covance scientific team. The eCRF and ancillary data will be converted into final SAS[®] datasets following Study Data Tabulation Model or client-provided specifications. The final datasets structure will be verified using Web Submission Data Manager[®], while the dataset content will be peer reviewed by an independent programmer.

The tables, figures, and listings (TFLs) will be programmed per the final SAP. All TFLs will be peer reviewed by an independent programmer. In addition, draft TFLs will be reviewed by the Covance scientific team during the dry run and data review meetings.

The peer review will be performed by independent programmers following the quality control process and programming checklists.

8.6. Quality Control and Quality Assurance

Quality control and quality assurance will be performed according to Covance standard operating procedures or per client request, and as applicable, according to the contract between Covance and the Sponsor.

9. ADMINISTRATIVE ASPECTS

9.1. Change in Protocol

There will be no alterations in the protocol without agreement between the Sponsor and the Investigator (or designee).

There will be no alterations in the protocol affecting subject safety without the express written approval of the Sponsor, Investigator (or designee), and the IRB (see Form FDA 1572).

9.2. Site Initiation Visit/Investigator Meeting

Prior to the start of the clinical study, the representative(s) of the Sponsor will meet with the Investigator (or designee) and appropriate clinical staff to familiarize the Investigator (or designee) and clinical staff with the materials necessary for conducting the clinical study.

9.3. Disclosure

All information provided regarding the study, as well as all information collected/documented during the study, will be regarded as confidential. The Investigator (or designee) agrees not to disclose such information in any way without prior written permission from the Sponsor.

Any publication of the results, in part or in total (eg, articles in journals or newspapers, oral presentations, abstracts) by the Investigator (or designee) or their representative(s), shall require prior notification and review, within a reasonable timeframe, by the Sponsor, and cannot be made in violation of the Sponsor's confidentiality restrictions or to the detriment of the Sponsor's intellectual property rights.

9.4. Monitoring

The Sponsor will designate a Study Monitor who will be responsible for monitoring this clinical trial. The Sponsor's Study Monitor will monitor the study conduct, proper eCRF and source documentation completion and retention, and accurate study drug accountability. To this end, the Sponsor's Study Monitor will visit the CRU at suitable intervals and be in frequent contact through verbal and written communication. It is essential that the Sponsor's

Study Monitor has access to all documents (related to the study and the individual participants) at any time these are requested. In turn, the Sponsor's Study Monitor will adhere to all requirements for subject confidentiality as outlined in the ICF. The Investigator (or designee) and Investigator's staff will be expected to cooperate with the Sponsor's Study Monitor, to be available during a portion of the monitoring visit to answer questions, and to provide any missing information.

9.5. Institutional Review Board

In accordance with US Title 21 Code of Federal Regulations (CFR) 56, the protocol, advertisement, ICF, and other information provided to subjects will be reviewed and approved by the IRB. The Sponsor will supply relevant material for the Investigator (or designee) to submit to the IRB for the protocol's review and approval. Verification of the IRB unconditional approval of the protocol and the written ICF statement will be transmitted to the Investigator (or designee).

The IRB will be informed by the Investigator (or designee) of subsequent protocol amendments and of serious and unexpected AEs. Approval for protocol amendments will be transmitted in writing to the Investigator (or designee). If requested, the Investigator (or designee) will permit audits by the IRB and regulatory inspections by providing direct access to source data/documents.

The Investigator (or designee) will provide the IRB with progress reports at appropriate intervals (not to exceed 1 year) and a Study Progress Report following the completion, termination, or discontinuation of the Investigator's (or designee's) participation in the study.

